16.3.9.3. Information to be Provided by the Investigator

SAEs for all enrolled subjects must be recorded on the SAE form (during study participation). This requirement includes all SAEs that occur after informed consent and through 28 days after last dose of study drug, and in addition, any SAEs that are assessed as possibly related to study drug by the investigator, even if the SAE occurs more than 28 days after the last dose of study drug must be reported to the Kadmon Corporation Pharmacovigilance Department (or designee).

The minimum information required for SAE reporting includes identity of investigator, site number, subject number, an event description, SAE term(s), onset date, the reason why the event is considered to be serious (ie, the seriousness criteria) and the investigator's assessment of the relationship of the event to study drug. Additional SAE information including medications or other therapeutic measures used to treat the event, action taken with the study drug due to the event, and the outcome/resolution of the event will be recorded on the SAE form. Forms for reporting SAE will be provided to the study sites.

In all cases, the investigator should continue to monitor the clinical situation and report all material facts relating to the progression or outcome of the SAE. Furthermore, the investigator may be required to provide supplementary information as requested by the Kadmon Corporation Drug Safety personnel or designee.

When reporting SAE, the following additional points should be noted:

- When the diagnosis of an SAE is known or suspected, the investigator should report the diagnosis or syndrome as the primary SAE term, rather than as signs or symptoms. Signs and symptoms may then be described in the event description. For example, dyspnea should not be used as an SAE term if the diagnosis which caused the dyspnea is known to be malignant pleural effusion.

- Death should not be reported as an SAE, but as an outcome of a specific SAE, unless the event preceding the death is unknown. In the exceptional case where the events leading to death are unknown, then death may be used as an event term. If an autopsy was performed, the autopsy report should be provided.
- While most hospitalizations necessitate reporting of an SAE, some hospitalizations do not require SAE reporting, as follows:
 - Elective or previously scheduled surgery (eg, a previously scheduled ventral hernia repair)
 - Procedures for pre-existing conditions that have not worsened after initiation of treatment
 - Pre-specified study hospitalizations for observation
 - Events that result in hospital stays of less than 24 hours and that do not require admission (eg, an emergency room visit for hematuria that results in a diagnosis of cystitis and discharge to home on oral antibiotics)
 - SAEs must, however, be reported for any surgical or procedural complication resulting in prolongation of the hospitalization.

16.3.9.4. Regulatory Reporting

Kadmon Corporation Drug Safety (or designee) will process and evaluate all SAEs as soon as the reports are received. For each SAE received, Kadmon Corporation will make a determination as to whether the criteria for expedited reporting have been met.

Kadmon Corporation (or designee) will submit SAEs that meet the criteria for expedited reporting to the Regulatory Authorities in accordance with local regulations governing safety reporting. Reporting of SAEs by the investigator to his or her IRB/IEC will be done in accordance with the standard operating procedures and policies of the IRB/IEC. Adequate documentation must be maintained showing that the IRB/IEC was properly notified.

16.4. Other Safety Considerations

16.4.1 Laboratory Data

All laboratory data obtained during the course of the study should be reviewed. Any abnormal value that leads to a change in subject management (eg, dose reduction or delay, requirement for additional medication or monitoring) or is considered to be of clinical significance by the investigator should be reported as an AE and/or SAE as appropriate, unless this value is

consistent with the subject's present disease state or is consistent with values obtained before entry into the study.

Laboratory results will be classified using the CTCAE v4.03.

16.4.2 Medication Errors

Any medication error that results in an AE, even if it does not meet the definition of serious, requires reporting within 24 hours to the safety monitor.

16.4.3 Follow-Up of Adverse Events

Any SAE or AE assessed as at least possibly related that led to treatment discontinuation (including clinically significant abnormal laboratory values that meet these criteria) and is ongoing 28 days after last dose of study drug must be followed until either resolution of the event or determination by the investigator that the event has become stable or irreversible. This follow-up guidance also applies to possibly related SAEs that occur *more than 28 days after last dose* of study drug. The status of all other continuing AEs will be documented as of 28 days after last dose of study drug.

17. STATISTICAL CONSIDERATIONS

All descriptive and inferential statistical analyses will be performed using SAS[®] (SAS Institute, Cary, North Carolina) statistical software, unless otherwise noted. For categorical variables, the number and percent of each category within a parameter will be calculated for non-missing data. For continuous variables, the mean, median and standard deviation, as well as the minimum and maximum values, will be presented.

Statistical significance will be declared when the *P* value is found to be ≤ 0.05 , unless otherwise noted. All clinical data captured will be provided in data listings.

17.1. General Design

All data for enrolled subjects will be presented in data listings by subject number. For those summary tables in which baseline and change from baseline measurements will be presented, the last observed measurement prior to the initial dose of KD025 will be considered the baseline measurement.

Continuous data will be described using descriptive statistics: number of observations (*n*), mean, standard deviation, median, minimum and maximum. Frequencies and percentages will be used for summarizing discrete (categorical) data. When categorical data are presented, the percent will be suppressed when the count is zero in order to draw attention to the nonzero counts. The denominator for all percentages, unless otherwise specified, will be the number of subjects in the specified analysis population. Two-sided 95% confidence interval employing the exact binomial method will be provided for activity outcomes.

Hypothesis testing, if appropriate, will be carried out at the 5% (2-sided) significance level. Because of the exploratory nature of the study, no adjustments will be made for the multiplicity of endpoints. Nonparametric tests may be used in preference to parametric tests if parametric assumptions are notably violated. Missing values will not be imputed. If a subject does not have sufficient data for a particular analysis, they will be excluded from that analysis. Endpoints defined as an average of multiple measurements will be used those data points that are non-missing, and the denominator was adjusted accordingly.

17.2. Sample Size Justification

The total sample size of 16 subjects per KD025 dose group will provide > 90% probability of one or more KD025 subjects experiencing an AE that has an underlying rate of $\geq 14\%$ and > 80% probability of one or more subjects in the study experiencing an AE that has an underlying rate of $\geq 10\%$.

Assuming an underlying 25% rate for subjects to meet the ORR, each treatment group of 16 subjects has an approximately 80% chance of having at least 3 subjects meet the overall response criteria, and approximately 90% chance of at least 2 subjects meet the overall response criteria.

17.3. Statistical Considerations

The statistical methodology will be further described in a Statistical Analysis Plan, which will be finalized prior to database lock.

17.3.1 Study Populations

Four populations will be employed in the analysis of study data:

- The modified intent-to-treat (mITT) population will consist of all subjects who are enrolled in the study and receive at least 1 dose of study medication.
- The safety population will consist of all subjects who receive at least one dose of KD025
- The PK population which will consist of all subjects who receive at least one dose of study drug and have at least 1 post-dose PK sample drawn

17.3.2 Subject Accountability, Demographics, and Baseline Characteristics

Demographics, subject disposition, and screening and baseline characteristics will be summarized for the mITT population.

17.3.3 KD025 Exposure

The amount of KD025 administered by visit and overall will be tabulated and presented by subject in data listings. In addition, delays and all other alterations in KD025 administration will be presented.

17.3.4 Concomitant Medications

Concomitant medications will be coded using WHO-DD and the data will be summarized by treatment group and presented in tables and listings.

17.4. Activity Analysis

The primary activity outcome will be the percentage of subjects who meet the OR criteria (PR + CR). This will be assessed overall (ie, any subject meeting the PR or CR criteria at any time point). For clarity, addition of new systemic therapy for cGVHD will be considered a KD025 treatment failure and will be considered progression of cGVHD for analysis purposes.

Secondary Endpoints

- Number and percentage of KD025 in subjects with steroid-dependent cGVHD who have a best response of PR or CR
- Change in cGVHD severity as based on the Physician-reported Global cGVHD Activity Assessment
- Change in symptom activity as based on cGVHD Activity Assessment Patient Self-Report
- Median FFS will be defined as the time from first dose of study drug to either the start of another treatment, relapse of the underlying disease, or death.
- Changes in corticosteroid and calcineurin inhibitor dose
- To evaluate DOR, which will be defined as the time of initial response until documented progression.
- To evaluate response by organ system. The response by organ system (PR and CR) will be assessed based on the 2014 NIH Consensus Development Project on Clinical Trials in cGVHD.
- Analyses of plasma PK of KD025 in subjects with cGVHD
- OS will be defined as the time from first dose of KD025 to the date of death due to any cause. Kaplan-Meier plots, descriptive statistics of OS and landmark OS at 6, 12, 18 and 24 months will be provided.
- TTNT will be defined as the defined as the time from the first dose of KD025 to the start of additional systemic cGVHD therapy Change in symptom burden/bother using the Lee cGVHD Symptom Scale.

Exploratory Endpoints

- Changes in the expression of several cytokines (including IL-17A, IL-21, and IL-2) in plasma after KD025 administration to subjects with cGVHD
- Changes in percentage of immune-cell subtypes (including Th17 and Treg cells) in whole blood after KD025 administration to subjects with cGVHD

17.5. Safety Data

The primary safety endpoint is the percent of subjects experiencing AEs in Cohort 1 (200 mg QD), Cohort 2, (200 mg BID), and Cohort 3 (400 mg QD).

Safety assessments include AEs, SAEs, PEs, vital sign measurements, clinical laboratory evaluations (including TSH measurements), ECGs, PFTs, and reasons for treatment discontinuation due to toxicity.

Treatment-emergent AEs will be evaluated using the CTCAE v4.03. The secondary safety outcome will be the number and percent of subjects experiencing AEs overall. The total sample size of 16 subjects per KD025 dose group will provide > 90% probability of one or more KD025 subjects experiencing an AE that has an underlying rate of $\geq 14\%$ and > 80% probability of one or more subjects in the study experiencing an AE that has an underlying rate of $\geq 10\%$.

Treatment-emergent AEs will be summarized by treatment group using Medical Dictionary for Regulatory Activities (MedDRA[®]) System Organ Class (SOC) and preferred term, classified from verbatim terms. MedDRA[®] Version 20.0 or higher will be used. The incidence and percentage of subjects with at least 1 occurrence of a preferred term will be included. The number of events per preferred term will also be summarized. Causality (relationship to study treatment) will be summarized separately.

All AEs, SAEs, treatment-related AEs, treatment-related SAEs, \geq Grade 3 AEs, treatment-related \geq Grade 3 AEs, and AEs leading to withdrawal, or treatment discontinuation will be summarized overall and by treatment group according to SOC and preferred terms. AEs will also be presented in listings. Duration of AEs will be determined and included in listings, along with action taken and outcome.

Laboratory results will be classified using the CTCAE v4.03 and summarized by treatment group. Incidence of laboratory abnormalities will be summarized. The worst on-study grade after

the first dose of study drug will be summarized. The incidence of \geq Grade 3 laboratory abnormalities under treatment and shifts in toxicity grading from baseline to highest grade post-baseline will be displayed.

Vital sign measurements will be summarized by treatment group at each scheduled time point using descriptive statistics.

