Safety Evaluation	Safety assessments include AEs, serious adverse events (SAEs), PEs, vital sign measurements, clinical laboratory evaluations (hematology, chemistry, and urinalysis), pulmonary function tests (PFTs), and ECGs.

	
Prior to enrolling subsequent cohorts, the safety data in each previous cohort will be evaluated after 8 subjects have reached 2 months of treatment to assure there is no safety signal. Two months was selected as the time for the safety review because all of the clinically significant KD025-related AEs to date occurred within 36 days or less of starting KD025 treatment.
 
The AE reporting period for a subject enrolled in the study begins when the subject provides informed consent and is continued through 28 days after their last dose of study drug. All AEs that occur in enrolled subjects during the AE reporting period must be recorded, regardless of the relationship of the AE to study drug. Any known untoward event that occurs beyond the AE reporting period that the investigator assesses as at least possibly related to study drug also should be reported to Kadmon. A Follow-Up Visit will occur 28 days after the last dose of study drug, but prior to starting on a new therapy if a new therapy is started earlier. This visit may be done within ± 7 days of the scheduled visit.
 
Exacerbation of any of the signs or symptoms of the disease will constitute a potential rationale for cessation of therapy. Both laboratory and clinical data may constitute a reason to pause or cease therapy. Previous studies have indicated that reversible and modest liver toxicity may occur spontaneously after a few weeks of initiation of therapy.
 
 • When treatment-related Grade 3 toxicities occur, drug administration will be halted until recovery to at least Grade 1, and study drug may be resumed at a reduced dose. • When treatment-related Grade 2 toxicities other than liver toxicities that cannot definitively be attributed to a cause other than the study drug occur, drug administration will be halted until recovery to at least Grade 1 at which time study drug administration may resume at the same dose. • When greater than Grade 2 liver toxicities occur, drug administration will be halted until recovery to at least Grade 1 at which time study drug administration may resume at a reduced dose. 
Pauses in therapy may not last more than 14 days; subjects requiring pauses of more than 14 days will be discontinued from the study. If Grade 2 or 3 treatment-related toxicities persist for 14 days, subjects will be discontinued from the study.
 
Other organ-based toxicity has not been observed in clinical studies with KD025, but as this is the first study in cGVHD, careful monitoring of all toxicities will be carried out. CTCAE v4.03 grading will be used for all AEs.

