6.3. Overview of Study Design

This is a Phase 2a, dose-escalation, open-label study designed to evaluate the safety, tolerability, and activity of KD025 in subjects with steroid-dependent cGVHD and active disease in terms of PR and CR as defined by the 2014 NIH Consensus Development Project on clinical trials in cGVHD (see [Appendix B](#)). This study also is designed to use the Physician-reported global cGVHD Activity Assessment to evaluate cGVHD severity; use the cGVHD Activity Assessment Patient Self-Report to assess symptom activity (see [Appendix C](#)); evaluate FFS; evaluate OS; assess changes in corticosteroid and calcineurin inhibitor (CNI) dose; evaluate TTNT; and assess the PK of KD025 in subjects with cGVHD. Changes in symptom burden/bother will be documented using the Lee cGVHD Symptom Scale (see [Appendix D](#)). Changes in the expression of several cytokines (including IL-17A, IL-21, and IL-2) in plasma and percentages of immune-cell subtypes (including Th17 and Treg cells) in whole blood after KD025 administration to subjects with cGVHD.

Subjects who have signed an IRB/IEC-approved informed consent form, and met all of the inclusion/exclusion criteria ([Section 7.2](#) and [7.3](#)), will be enrolled. Approximately 48 subjects will receive orally administered KD025 200 mg QD (n = 16), KD025 200 mg BID (n = 16), or KD025 400 mg QD (n = 16). Study drug will be administered in 28-day cycles until disease progression or unacceptable toxicity occurs. For disease progression, subjects with a “Lack of Response (LOR) – Mixed” response assessment ([Appendix B](#)) may continue treatment with KD025 and remain on study if the investigator considers continued treatment to be in the subject’s best interest, only after approval from the medical monitor and documentation of the subject’s willingness to continue. Subjects may receive study drug treatment either in the inpatient or outpatient setting.

Prior to enrolling subsequent cohorts, the safety data in each previous cohort will be evaluated after 8 subjects have reached 2 months of treatment to assure there is no safety signal. As this is an open-label study, safety data will be continuously monitored. If $\geq 25\%$ of subjects in a cohort experience a [Common Terminology Criteria for Adverse Events \(CTCAE\)](#) v4.03 Grade 2 liver toxicity or a CTCAE v4.03 Grade 3 (or higher) AE in the same organ or body system, or if

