## **2.2 Study Design**

This is a Phase 2a, open-label, dose-escalation, safety, tolerability, and activity study.

Subjects who have signed an Institutional Review Board/Independent Ethics Committee-approved informed consent form and who have met all of the inclusion/exclusion criteria will be enrolled. After approximately 4 weeks for screening, subjects will receive KD025 orally (PO) in 28-day cycles until disease progression or unacceptable toxicity occurs followed by 4 weeks of follow-up. In addition, subjects will be contacted every 8 weeks until study close-out to confirm survival status and the initiation of any anticancer treatment or any changes in treatment for cGVHD.

Sequential cohorts of approximately 16 subjects will be dosed at KD025 200 mg once daily (QD) PO, KD025 200 mg twice daily (BID) PO, and KD025 400 mg QD (Table 1). Prior to enrolling subsequent cohorts, the safety data in each previous cohort will be evaluated after 8 subjects have reached 2 months of treatment.

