#### **3.9.1 Adverse Events**

AEs will be coded using the MedDRA dictionary (Version 20.1 or higher). Treatment-emergent AEs (TEAEs) are any AE occurring or worsening in severity after the first administration of study medication. All AEs (including SAEs) will be graded using the 5-point Common Terminology Criteria for Adverse Events (CTCAE) V5.0 scale (mild, moderate, severe, life-threatening, or death). Causality with KD025 will be classified as: definitely related; probably related; possibly related; unlikely related; or not related.

The investigator will further assess the relationship of AEs to cGVHD or the underlying disease.

The number and percentage of patients who experienced at least one TEAE as well as the number and percentage of patients who experienced AEs of each specific SOC and PT will be presented. For the presentation of AE incidences, the SOCs and the PTs within each SOC will be presented by decreasing total frequency. Tabulation by maximum severity and relationship to KD025 will also be included by treatment group.

The TEAEs, Grade  $\geq 3$  TEAEs, SAEs, and TEAEs leading to dose modification/discontinuation will be summarized by treatment arm, SOC, and PT. These analyses will be repeated for events considered related (definitely related/probably related/possibly related) to KD025.

Subject listings will be provided for SAEs, AEs resulting in study drug discontinuation and deaths.

Adverse events will also be presented in listings. Time to onset and duration of AEs will be included in listings, along with action taken and outcome.

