### **3.14 Primary CSR Analysis**

A primary CSR analysis will be conducted 1 year after the last subject is enrolled.

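### The primary safety endpoint and the by-cohort AE tables are unadjusted percentages over open-ended, unequal exposure, so cohort differences cannot be separated from time on drug

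*Protocol*

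**What the plan says.** The endpoint is defined in Protocol 17.5: "The primary safety endpoint is the percent of subjects experiencing AEs in Cohort 1 (200 mg QD", with Cohorts 2 and 3 named in the same sentence. The same section pools the measure: "The secondary safety outcome will be the number and percent of subjects experiencing AEs overall". Neither sentence sets a time window, a grade or a relatedness limit. SAP 3.9.1 tabulates "The number and percentage of patients who experienced at least one TEAE", and gives the same kind of summary by SOC and preferred term, by maximum severity, and for Grade 3+, serious, related and dose-modifying events.

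Four design features decide how long each subject can contribute an AE:

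- Treatment length (Protocol 6.3): "Study drug will be administered in 28-day cycles until disease progression or unacceptable toxicity occurs".
- AE collection (Protocol synopsis, Safety Evaluation): it "begins when the subject provides informed consent and is continued through 28 days after their last dose of study drug", so it lengthens with time on drug.
- Cohort order (SAP 2.2): "Sequential cohorts of approximately 16 subjects will be dosed at KD025 200 mg once daily (QD) PO", followed by the other two regimens. "Prior to enrolling subsequent cohorts, the safety data in each previous cohort will be evaluated after 8 subjects have reached 2 months of treatment".
- Data cut (SAP 3.14): "A primary CSR analysis will be conducted 1 year after the last subject is enrolled".

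The plan is not silent on exposure. SAP 3.7 summarises treatment duration, SAP Table 3 lists a follow-up duration table, and SAP 3.9.1 puts time to AE onset in listings. None of these enters an AE summary as a denominator or a window. Protocol 17.5 also plans event counts per preferred term, which grow with exposure as well.

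**The concern.** Safety and tolerability of KD025 is a primary objective, and Protocol 4.2 says that the two 400 mg/day cohorts are there to examine dosing frequency. Readers will therefore set the cohort columns side by side, whether or not a test is planned.

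An unadjusted percentage of subjects with an event rises with time at risk. Two things can make time at risk differ between cohorts here. Calendar time is one: an earlier cohort has longer potential follow-up at a single cutoff. Retention is the other: subjects who do well stay on drug and stay under AE collection. Either can make one regimen look less safe than another that has the same event rate.

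Separately, an any-AE percentage with no window may approach its ceiling and lose its ability to distinguish cohorts.

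**Working it through.** **1. The plan's own figures.** Protocol 17.5 and SAP 3.12 give more than 90% and more than 80% probability of seeing at least one subject with an AE whose underlying rate is 14% or 10%. With n = 16:

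- 1 − (1 − 0.14)^16 = 91.0%
- 1 − (1 − 0.10)^16 = 81.5%

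Both reproduce. The rate is a per-subject probability with no time period attached, which is the same gap as in the endpoint.

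**2. Unequal potential follow-up.** From SAP 2.2, each new cohort waits until 8 subjects of the previous one have had 2 months of treatment. Two such waits separate Cohorts 1 and 3: 2 × 2 = 4 months, before any accrual time. The documents give no accrual rate, so a 12-month gap is shown as a larger assumed case. From SAP 3.14, the last subject has 12 months of potential follow-up; 15 months is assumed as typical for the last cohort.

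**3. Same hazard, different follow-up.** Let h be the Grade 3+ first-event hazard, d the discontinuation rate and T the potential follow-up in years. The documents give neither h nor d; both are assumed constant and equal across cohorts, and the 28-day tail after the last dose is ignored. The expected crude percentage is

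h/(h + d) × (1 − exp(−(h + d)T)).

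For h = d = 0.5 and T = 1.25 this is 0.5 × (1 − exp(−1.25)) = 0.5 × (1 − 0.2865) = 35.7%. With d = 0.5 throughout:

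| h per year | 15 months | 19 months (4-month gap) | 27 months (12-month gap) |
|---|---|---|---|
| 0.25 | 20.3% | 23.2% | 27.2% |
| 0.5 | 35.7% | 39.7% | 44.7% |
| 1.0 | 56.4% | 60.5% | 64.4% |

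At h = 0.5 the spurious difference is 4.0 points (about 0.65 of a subject in 16) for the 4-month gap, and 9.0 points (about 1.4 subjects) for the 12-month gap.

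**4. Same hazard, same follow-up, different retention.** Take T = 1.25 and h = 0.5, with d = 1.2 in one cohort and 0.5 in another:

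- d = 1.2: 0.5/1.7 × (1 − exp(−2.125)) = 25.9%
- d = 0.5: 35.7%

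The better-retained cohort looks about 10 points worse. With h from 0.25 to 1.0 the gap runs from about 6 to 14 points.

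**5. Possible saturation of the any-AE percentage.** Let q be the assumed risk of a first AE per 28-day cycle. The percentage after c cycles is 1 − (1 − q)^c. Doubling the hazard replaces (1 − q)^c by (1 − q)^(2c).

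| q | After 12 cycles | Points shown by a doubled hazard, 12 cycles | Same, first 2 cycles |
|---|---|---|---|
| 0.1 | 72% | 20 | 15 |
| 0.2 | 93% | 6 | 23 |
| 0.3 | 99% | 1 | 25 |

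At q = 0.1 there is no ceiling problem at 12 cycles; at q = 0.3 there is.

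**The case against.** Most of the case on the other side concerns how far the point reaches, and much of it stands.

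- **No stated decision uses this percentage.** The escalation and stopping rules (Protocol 6.3, 13.3 and 14.2) rest on Grade 2 liver toxicity, Grade 3+ events in one organ system, and discontinuations. No between-cohort AE test is specified, the cohorts are not randomized, and the analysis is called exploratory. This stands and limits the consequence.
- **The plan has more than subject percentages.** Treatment and follow-up duration are tabulated, and liver tests are shown by visit and cohort, which compares cohorts at common times. This stands for laboratory values. It does not help the AE tables: the Grade 3+, serious and related summaries are crude too.
- **A reader might infer that the any-AE percentage will end near 100% and could not reveal a doubled rate.** The documents give no any-AE rate or time on drug for this population. At q = 0.1, a doubling over 12 cycles still shows as 20 points.
- **A reader might infer that any cohort difference would merely reflect time on drug.** Actual exposure by cohort is unknown, so the two are mixed; the documents do not show that exposure dominates. The two effects also pull apart: once a percentage saturates, little cohort difference is left to explain.
- **The remedy is imprecise at this size.** With h = d = 0.5, Grade 3+ within 2 cycles is 7.1%, or 13.7% if the hazard doubles: 1.1 vs 2.2 subjects of 16. Six first events carry an exact Poisson interval of 2.2 to 13.1. This stands. The added tables remove an exposure bias; they do not supply precision.

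**Conclusion.** The point holds as a reporting weakness. The primary safety endpoint and the by-cohort TEAE tables take no account of time at risk, and the design makes time at risk unequal, so dose and time on drug cannot be told apart in them. On the assumed rates, identical Grade 3+ hazards produce a 4-point difference at the minimum gap implied by the cohort rule and a 9-point difference at a 12-month gap. These sizes rest on constant hazards, on 15 months of potential follow-up in the last cohort, and on assumed event and discontinuation rates. Saturation is a possibility that depends on the AE rate. The change is worth making because it is cheap and safety is a primary objective. Nothing in the escalation rules or the planned inference is invalidated.

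**What to change.** Keep the crude tables and the protocol endpoint. Add to SAP 3.9.1 and SAP Table 6, by cohort, for any, Grade 3+, serious and related TEAEs:

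- (a) the number and percentage of subjects with a first event in a common window: the first 2 cycles (56 days), matching the 2-month safety review in Protocol 14.2, and the first 6 cycles (168 days), which fits inside the 1-year minimum potential follow-up;
- (b) first events per patient-year at risk, with an exact Poisson 95% CI.

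State that these are the figures to use when cohorts are described side by side.

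The cost is a few tables built from AE onset and dosing dates already collected. Protocol 17.3 leaves further methodology to the SAP, so adding supportive tables there leaves the protocol endpoint unchanged; rewording Protocol 17.5 itself would need an amendment. The limits should be stated. Window (a) equalises potential follow-up, but subjects who stop early remain in the denominator. Rate (b) assumes a roughly constant hazard, which (a) helps to check. Intervals will be wide with 16 subjects per cohort, so the results remain descriptive.
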